17.2.2 Void Data Derivations

• For baseline and posttreatment visits, analyses on void diary efficacy variables will be based on the diary data collected during a 3-day interval for each visit. Each 3-day interval consists of 3 consecutive 24-hour periods, with the first period starting from the time of the first urinary episode on the first of the 3 days.

- A valid diary day is defined as any of the three 24-hour periods with 2 or more urinary episodes. Data collected from a 24-hour period with less than 2 urinary episodes (i.e., an invalid diary day) will be set to missing.
- For baseline and posttreatment visits, the 3-day diary will be determined based on the following algorithm:
 - Apply visit windows defined in Section 17.1, which are based on days from the date of study first treatment in each treatment period.
 - Determine the time of the first urinary episode that is within the visit window (in the example below, 7:30 am on April 3). Count forwards for 3 consecutive days. Note: the last 24-hour period should end within the window, i.e., prior to or on the last day specified in the window definition; otherwise, the 24-hour data will not be used for the corresponding window. For baseline diary data, the urinary episodes that occurred on the day of first IP insertion but before the IP insertion time will be counted as baseline diary data.
 - Using the example below, the first 24-hour time period starts from 7:30am on April 3 and ends at 7:29 am on Apr 4. The second 24-hour time period starts from 7:30am on Apr 4 and ends at 7:29 am on Apr 5. Note that this 24-hour is considered as an invalid diary day since it has just one episode during the 24 hours. The third or the last 24-hour time period starts from 7:30 am on Apr 5 and ends at 7:29 am on Apr 6.
 - At least one valid 24-hour diary day within the window is required for the visit. Otherwise, the 3-day diary data will be missing for the visit.

17.3 **REPEATED OR UNSCHEDULED ASSESSMENTS OF SAFETY PARAMETERS**

If a patient has repeated assessments before the start of the first treatment, the results from the final non-missing assessment made prior to the start of the study treatment will be used as baseline.

17.4 MISSING DATE OF THE LAST DOSE OF STUDY TREATMENT

Not applicable.

17.5 MISSING SEVERITY ASSESSMENT FOR ADVERSE EVENTS

If severity is missing for an AE that started before the date of the first dose of study treatment, an intensity of mild will be assigned. If severity is missing for an AE that started on or after the date of the first dose of study treatment, an intensity of severe will be assigned. The imputed values for severity assessment will be used for the incidence summary; the values will be shown as missing in the data listings.

17.6 MISSING CAUSAL RELATIONSHIP TO STUDY TREATMENT FOR ADVERSE EVENTS

If the causal relationship to the study treatment is missing for an AE that started on or after the date of the first dose of study treatment, a causality of yes will be assigned. The imputed values for causal relationship to study treatment will be used for the incidence summary; the values will be shown as missing in the data listings.

17.7 MISSING DATE INFORMATION FOR ADVERSE EVENTS

The following imputation rules only apply to cases in which the start date for AEs is incomplete (i.e., partly missing).

Missing month and day

- If the year of the incomplete start date is the same as the year of the first dose of study treatment, the month and day of the first dose of study treatment will be assigned to the missing fields
- If the year of the incomplete start date is before the year of the first dose of study treatment, *December 31* will be assigned to the missing fields
- If the year of the incomplete start date is after the year of the first dose of study treatment, *January 1* will be assigned to the missing fields

Missing month only

• If only the month is missing, the day will be treated as missing and both the month and the day will be replaced according to the above procedure

Missing day only

- If the month and year of the incomplete start date are the same as the month and year of the first dose of study treatment, the day of the first dose of study treatment will be assigned to the missing day
- If either the year of the incomplete start date is before the year of the date of the first dose of study treatment or if both years are the same but the month of the incomplete start date is before the month of the date of the first dose of study treatment, the last day of the month will be assigned to the missing day
- If either the year of the incomplete start date is after the year of the date of the first dose of study treatment or if both years are the same but the month of the incomplete start date is after the month of the date of the first dose of study treatment, the first day of the month will be assigned to the missing day

If the stop date is complete and the imputed start date as above is after the stop date, the start date will be imputed by the stop date.

If the start date is completely missing and the stop date is complete, the following algorithm will be used to impute the start date:

- If the stop date is after the date of the first dose of study treatment, the date of the first dose of study treatment will be assigned to the missing start date
- If the stop date is before the date of the first dose of study treatment, the stop date will be assigned to the missing start date

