12.0 SAFETY ANALYSES

The safety analysis will be performed using the Safety Population. The safety parameters will include adverse events (AEs) and clinical laboratory and vital signs parameters, physical and pelvic assessments. For each clinical laboratory and vital sign parameters, the last non-missing safety assessment before the first Treatment 1 IP insertion will be used as the baseline for all analyses of that safety parameter. Continuous variables will be summarized by number of patients and mean, SD, median, minimum, and maximum values. Categorical variables will be summarized by number of patients.

All safety analyses will be performed using the safety population. For such analyses, subjects will be analyzed according to actual treatment received at the study treatment visit (i.e., "as treated" rather than "as randomized").

The following safety analyses will be performed unless otherwise mentioned:

- Summaries by treatment group and overall for the Treatment 1 period
- Summaries for patients who participated in both the Treatment 1 period and Treatment 2 period by treatment group and overall patient population. In this analysis, the treatment groups will be the safety treatment groups.

12.1 **ADVERSE EVENTS**

Adverse events will be coded by system organ class and preferred term using the *Medical Dictionary for Regulatory Activities*, version 18.1 or newer.

An AE will be considered a treatment-emergent adverse event (TEAE) if it was present after the first dose of study treatment or was present before the date of the first dose of study treatment and increased in severity after the first dose of study treatment or became serious after the first dose of study treatment. If more than 1 AE was reported before the first dose of study treatment and coded to the same preferred term, the AE with the greatest severity will be used for comparison with the AEs occurring during the study period.

Analysis of the incidence of TEAEs will be performed for the Treatment 1 Period using the Safety population. For the cohort of safety patients that received Treatment 2 IP, the incidence of TEAEs will be summarized over the Treatment 2 Period and over the entire study period (Treatment 1 and 2 period). The following rules will be used to count TEAEs at each treatment period.

- For the analyses of TEAEs by treatment period, an event will be counted once in the particular period if the onset of this event begins during that corresponding period.

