The data derivations and definitions listed in this section are to be applied to all analyses described in this analysis plan, unless otherwise stated.

- In this study there are two treatment periods:
 - Treatment period 1: for patients that just receive treatment in the randomized and blinded phase of the trial, it covers the period from the first Treatment 1 IP insertion to study exit. In contrast, for patients that receive IP insertions in both the randomized phase of the study (Treatment 1) and the open label phase of the study (Treatment 2) it covers the period from first Treatment 1 IP insertion up to Treatment 2 IP insertion,
 - Treatment period 2: covers the period from Treatment 2 IP insertion to study exit.
- Study days for each treatment period X (X=1 or 2) will be calculated as:
 - Study day of Treatment X = visit date (day 1 of Treatment X) + 1.
- The baseline value of an assessment will be the last value recorded prior to the patient being inserted with first Treatment 1 IP on Day 1.
- Unless otherwise stated no imputation will be performed for missing data. All analyses will be based on the observed data.
- For analyses that are by stratification factor, actual stratification levels rather than randomization stratification levels will be used.
- Data will be pooled across the investigational sites.
- Descriptive statistics for continuous/ordinal data include the sample size (N), mean, standard deviation (SD), median, minimum (Min), and maximum (Max) and 95% confidence intervals.
- Summary statistics for categorical variables include sample size (N), frequency count (n), and percentage (%).

17.2.1 **Pain Data Derivations**

A pain assessment tool will be utilized in the study to capture the average daily pain and the daily worst pain scores on an electronic hand held device. Patients will be asked to rate their daily pain on a pain NRS consisting of an 11 point integer scale ranging from 0 for "no pain" to 10 for "worst pain imaginable". The pain assessment will continue every day up to and including the day prior to the Exit visit.

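### SAP 17.7 completes partial or missing AE start dates without using the Treatment 2 insertion date, so an event that began on open-label LiRIS can be counted in Treatment 1

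*SAP*

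**What the plan says.** **Imputation (SAP 17.7).** Every branch compares the incomplete start date with the first dose. Treatment 2 insertion is not mentioned.

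- Day missing, month later than the first-dose month: "the first day of the month will be assigned to the missing day".
- Month and day missing, same year as first dose: "the month and day of the first dose of study treatment will be assigned to the missing fields".
- Month and day missing, later year: "If the year of the incomplete start date is after the year of the first dose of study treatment", 1 January of that year is used.
- Start fully missing, stop date after first dose: "the date of the first dose of study treatment will be assigned to the missing start date".
- A safeguard replaces the imputed start with the stop date, but only "If the stop date is complete and the imputed start date as above is after the stop date".

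**Period assignment (SAP 12.1 and 17.2).** For the by-period tables, "an event will be counted once in the particular period if the onset of this event begins during that corresponding period". For a retreated patient, Treatment 1 is defined so that "it covers the period from first Treatment 1 IP insertion up to Treatment 2 IP insertion". The other period is defined as follows: "Treatment period 2: covers the period from Treatment 2 IP insertion to study exit". SAP 12.1 adds that an event dated in Treatment 1 which continues into Treatment 2 without worsening or becoming serious is not counted again in Treatment 2.

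**What Treatment 2 is (SAP 5.0; Protocol 5.6.2).** Every retreated patient, whatever the Treatment 1 group, receives open-label LiRIS 400 mg for 14 days and is then observed for 4 weeks.

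**The concern.** Anchoring on the first dose is a cautious way to decide whether an event is treatment-emergent. This trial asks a second question of the same date: which side of Treatment 2 insertion does it fall on? The rules do not use that boundary, so for some incomplete dates they choose the earlier period regardless of when the patient was retreated.

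A placebo/placebo patient who is retreated receives LiRIS for the first time in Treatment 2. If an event from that period is back-dated past the insertion, it appears as a placebo event in the Treatment 1 table and is missing from Treatment 2 incidence. With 19 patients planned in that group, one patient wrongly added to a preferred term changes its incidence by 1/19, about 5 percentage points.

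The lidocaine special-interest table in SAP 12.1 can also be affected. For Treatment 1 it covers insertion up to the day after the second removal, that is days 0 to 29. An event set to the first-dose date falls inside that window.

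**Working it through.** **1. When Treatment 2 can start.** The plan states 16 to 36 weeks of participation for retreated patients.

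- Minimum: 2 (diary run-in, Protocol 6.5.12) + 4 (Treatment 1) + 4 (follow-up) + 2 (Treatment 2) + 4 (observation) = 16 weeks.
- Maximum: 4 (screening) + 4 + 20 + 2 (14-day rescheduling, Protocol 5.6.2) + 2 + 4 = 36 weeks.

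Both figures reproduce, the second with the rescheduling allowance included. On the two-device schedule, Treatment 2 insertion therefore falls between day 28 + 28 = 56 and day 28 + 140 + 14 = 182 after first insertion. The Treatment 2 period lasts 14 + 28 = 42 days.

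**2. Worked cases.**

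| First dose | Treatment 2 insertion | True onset | Missing | Imputed start | Counted in |
|---|---|---|---|---|---|
| 10 Mar | 15 Jun | 18 Jun | day | 1 Jun | Treatment 1 (wrong) |
| 10 Mar | 15 Jun | 5 Jul | day | 1 Jul | Treatment 2 (right) |
| 10 Mar | 15 Jun | 18 Jun | month and day | 10 Mar | Treatment 1 (wrong) |
| 10 Oct | 12 Dec | 9 Jan | month and day | 1 Jan | Treatment 2 (right) |

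The stop-date safeguard cannot repair the wrong cases. The imputed start precedes insertion, and insertion is no later than the true onset or the stop, so the condition is never met.

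**3. Share of true Treatment 2 onsets that move.** The documents give no AE timing. Assume that insertion is equally likely on any calendar day and that onset is uniform over N days counted from insertion day (N = 43 for days 0–42, 15 for days 0–14, 3 for days 0–2). L = 365/12 = 30.4 is the mean month length.

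*Day missing.* An event moves if onset is in the insertion month and insertion was not on the 1st. None is set to the first-dose date, because Treatment 2 starts at least 56 days later.

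- N = 43: (L − 1)/(2 × 43) = 29.4/86 = 34.2%
- N = 15: 1 − 8/L = 22.4/30.4 = 73.7%
- N = 3: 1 − 2/L = 28.4/30.4 = 93.4%

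*Month and day missing.* An event stays in Treatment 2 only if 1 January falls on or after insertion and on or before onset. The share that stays is ((N + 1)/2)/365.

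- N = 43: 1 − 22/365 = 94.0%
- N = 15: 1 − 8/365 = 97.8%
- N = 3: 1 − 2/365 = 99.5%

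*Start fully missing, stop date after Treatment 2 insertion.* The first-dose date is always assigned, so 100% move.

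Direct enumeration of the rules, with first doses spread over a year and insertion over days 56–182, gives 34.1%, 73.5% and 93.2% for day missing, and 94.0%, 97.8% and 99.5% for month and day missing. In the same enumeration, 69–75% of Treatment 2 events with month and day missing land on days 0–29 after first insertion, inside the Treatment 1 lidocaine window. So do all those with a fully missing start and a stop date after Treatment 2 insertion.

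**The case against.** A reader might infer that the SAP sends Treatment 2 events into Treatment 1 wholesale, or sets every incomplete date to the first dose. It does neither. Complete dates are untouched. With only the day missing over the full 42 days, about two thirds of events stay where they belong. A later year gives 1 January, which can fall in Treatment 2.

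A reader might also infer that a LiRIS excess is being hidden. The documents do not support a direction. Retreatment is at the patient's request, and no rate by group is given. If the LiRIS groups retreat more, their Treatment 1 figures rise instead.

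Several further limits stand:

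- Safety is analysed as treated, and no formal AE test is planned. Laboratory values and vital signs are also summarised by group, so AE percentages are not the only controlled safety information.
- A patient counts once per preferred term. A misdated event adds nothing to a Treatment 1 percentage if that patient already had the term in Treatment 1.
- The whole-study summary for retreated patients does not depend on the period boundary.
- AEs are queried at each visit (Protocol 9.1.1) and Treatment 2 is short. Events known only to the year should be rare, so the 94% probably applies to very few.
- The 73% supposes onset within 14 days of insertion, and the documents give no onset distribution.

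These points limit the size of the problem. None of them corrects the rule.

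**Conclusion.** The point holds as a limited defect. For retreated patients, SAP 17.7 can place an event that began on open-label LiRIS in the Treatment 1 as-treated summary and remove it from Treatment 2 incidence. It does so in three situations:

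- only the day is missing, the reported month is the Treatment 2 insertion month and insertion was not on the 1st;
- month and day are missing, in most cases;
- the start is fully missing and the stop date follows Treatment 2 insertion, in every case.

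The percentages are shares of the incompletely dated Treatment 2 events and rest on assumed uniform timing. How many such events exist is unknown and probably small, so the absolute effect may be nil or a few events. Efficacy, sample size and formal inference are untouched. It is worth correcting because a stated rule gives a wrong result in identifiable cases, and the SAP already uses the missing date in its duration formulas (SAP 10.1). The omission is certain; the size and direction of its effect are not.

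**What to change.** Add to SAP 17.7, for patients given Treatment 2, a rule for any partial or missing AE start date that is compatible with onset on or after Treatment 2 insertion and does not itself settle the period:

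1. If the stop date is before Treatment 2 insertion, assign Treatment 1.
2. Otherwise, if the event was first recorded at or before the AE query that precedes insertion at the insertion visit, assign Treatment 1.
3. If it was first recorded after insertion and is still unresolved, impute the Treatment 2 insertion date.

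Events resolved to Treatment 1 keep the existing imputation. A reported month or year wholly after insertion already settles the period, so the present rule can stand there.

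The cost is a short SAP addition and modest programming before database lock. The AE form is not in the documents, so it must be confirmed that the visit of first recording can be recovered. The downside is the reverse error: a few late Treatment 1 onsets first reported after insertion may be placed in Treatment 2. To keep this visible, list every AE whose period was imputed and, if any exist, show the Treatment 1 table under both assignments.

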17.8 MISSING DATE INFORMATION FOR PRIOR OR CONCOMITANT MEDICATIONS

For prior or concomitant medications, including rescue medications, incomplete (i.e., partly missing) start dates and/or stop dates will be imputed. When the start date and the stop date are both incomplete for a patient, the start date will be imputed first.

17.8.1Incomplete Start Date

The following rules will be applied to impute the missing numeric fields for an incomplete prior or concomitant medication start date. If the stop date is complete (or imputed) and the imputed start date is after the stop date, the start date will be imputed using the stop date.

Missing month and day

- If the year of the incomplete start date is the same as the year of the first dose of study treatment, the month and day of the first dose of study treatment will be assigned to the missing fields
- If the year of the incomplete start date is before the year of the first dose of study treatment, *December 31* will be assigned to the missing fields
- If the year of the incomplete start date is after the year of the first dose of study treatment, *January 1* will be assigned to the missing fields

Missing month only

• If only the month is missing, the day will be treated as missing and both the month and the day will be replaced according to the above procedure

Missing day only

- If the month and year of the incomplete start date are the same as the month and year of the first dose of study treatment, the day of the first dose of study treatment will be assigned to the missing day
- If either the year of the incomplete start date is before the year of the date of the first dose of study treatment or if both years are the same but the month of the incomplete start date is before the month of the date of the first dose of study treatment, the last day of the month will be assigned to the missing day.
- If either the year of the incomplete start date is after the year of the date of the first dose of study treatment or if both years are the same but the month of the incomplete start date is after the month of the date of the first dose of study treatment, the first day of the month will be assigned to the missing day

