9.0 PRIOR OR CONCOMITANT MEDICATION

Prior medication is defined as any medication taken before the date of the first IP insertion. *Concomitant medication* is defined as any medication taken on or after the date of first IP insertion. The WHO drug dictionary, version 2015 quarter 4 or newer, will be used to classify prior and concomitant medications by therapeutic class and drug name.

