17.8.2 Incomplete Stop Date

The following rules will be applied to impute the missing numeric fields for an incomplete prior or concomitant medication stop date. If the imputed stop date is before the start date (imputed or non-imputed start date), the imputed stop date will be equal to the start date.

Missing month and day

• If the year of the incomplete stop date is the same as the year of the last dose of study treatment, the month and day of the study exit date will be assigned to the missing fields

- If the year of the incomplete stop date is before the year of the last dose of study treatment, *December 31* will be assigned to the missing fields
- If the year of the incomplete stop date is after the year of the last dose of study treatment, *January 1* will be assigned to the missing fields

Missing month only

• If only the month is missing, the day will be treated as missing and both the month and the day will be replaced according to the above procedure

Missing day only

- If the month and year of the incomplete stop date are the same as the month and year of the last dose of study treatment, the day of the study exit will be assigned to the missing day
- If either the year of the incomplete stop date is before the year of the date of the last dose of study treatment or if both years are the same but the month of the incomplete stop date is before the month of the date of the last dose of study treatment, the last day of the month will be assigned to the missing day
- If either the year of the incomplete stop date is after the year of the date of the last dose of study treatment or if both years are the same but the month of the incomplete stop date is after the month of the date of the last dose of study treatment, the first day of the month will be assigned to the missing day

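### SAP 17.8.1 and 17.8.2 give opposite tie-breaks when a medication's start and stop dates are both partial, and the stated order can file a drug stopped before insertion as concomitant

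*SAP*

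**What the plan says.** SAP 17.8 applies to partly missing start and stop dates of prior and concomitant medications, rescue medication included. The relevant rules are these.

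- **Order (17.8).** "When the start date and the stop date are both incomplete for a patient, the start date will be imputed first".
- **Start rule (17.8.1).** If month and day are missing and the year is that of the first dose, "the month and day of the first dose of study treatment will be assigned to the missing fields". A start with only the month missing is handled the same way, because its day is then treated as missing too.
- **Start tie-break (17.8.1).** "If the stop date is complete (or imputed) and the imputed start date is after the stop date, the start date will be imputed" from the stop date.
- **Stop rule (17.8.2).** If only the day is missing and the recorded month is before that of the last dose, "the last day of the month will be assigned to the missing day".
- **Stop tie-break (17.8.2).** If the imputed stop falls before the start, whether that start was recorded or itself imputed, "the imputed stop date will be equal to the start date".
- **Classification (9.0).** Prior means taken before the first insertion. Concomitant medication "is defined as any medication taken on or after the date of first IP insertion".

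The SAP does not say which tie-break prevails.

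**The concern.** An imputed start and an imputed stop exist together only when both dates are partial. That is the one case in which both tie-breaks apply, and they pull in opposite directions. Under the stated order no imputed stop exists yet when 17.8.1 is applied to the start, so a program written step by step goes on to 17.8.2. The start placed at insertion by convention then overrides a stop month that the site actually recorded.

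Stopped drugs will be in the database, because Protocol 6.5.1 collects prior treatments and the reasons for stopping them. SAP 9.2 plans prior and concomitant tables for eCRF medications, with a further pair for pain medication identified there. A reader of a pain trial uses those tables to see what patients were taking during treatment. A drug that had already ended can move from one table to the other, and two programmers working from the same SAP could produce different tables.

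**Working it through.** The plan gives no figure to reproduce, so the check applies the rules to dates. The dates are illustrative assumptions: first insertion 15 Sep 2016, last dose 29 Sep 2016, start recorded as 2016 only, stop recorded as Feb 2016. First dose is read as first insertion.

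| Step | Rule | Start | Stop |
|---|---|---|---|
| 1 | Start first; year equals first-dose year (17.8.1) | 15 Sep 2016 | not yet imputed |
| 2 | Stop month before last-dose month (17.8.2) | 15 Sep 2016 | 29 Feb 2016 |
| 3a | Tie-break in 17.8.2 | 15 Sep 2016 | 15 Sep 2016 |
| 3b | Tie-break in 17.8.1, instead of 3a | 29 Feb 2016 | 29 Feb 2016 |

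Under SAP 9.0, 3a is concomitant and not prior, and 3b is prior only. The two results differ by 199 days, about 6.5 months.

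To find which records are affected, I applied both tie-breaks to a grid of constructed drugs that ended at least 60 days before insertion, with only the stop day missing. Entries are the number classed as concomitant under 17.8.2, out of the number of constructed records.

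| Start recorded as | Insertion 15 Mar 2016 | 15 Sep 2016 | 10 Dec 2016 |
|---|---|---|---|
| Year only, insertion year | 10/10 | 1353/1353 | 2755/2755 |
| Year only, earlier year | 0/7436 | 0/6093 | 0/4691 |
| Month and year, insertion year | 0/10 | 0/1353 | 0/2755 |
| Month and year, earlier year | 0/7436 | 0/6093 | 0/4691 |

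Under the 17.8.1 tie-break every cell is 0. The denominators count constructed date combinations, so they show which patterns fail and not how often such records occur.

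The zeros follow from the rules:

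- An earlier-year start with unknown month becomes 31 December of that year. The stop can be moved to that date, but the drug remains prior.
- A start with a known month before the insertion month becomes the last day of that month, which is never later than the last day of the stop month.
- If the stop date is complete, 17.8.1 caps the start and the drug remains prior.

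Three conditions are therefore needed together: start month missing, start year equal to the first-insertion year, and a recorded stop month before the insertion month.

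For scale, using the planned group sizes of 19 and 38: 1/19 = 5.3 percentage points and 1/38 = 2.6 percentage points per misfiled patient for a given drug, if that patient has no other record of it.

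**The case against.** The strongest reply is that this is an ambiguity and not a fixed error. Section 17.8.1 expressly provides for an imputed stop, and a programmer who applied it last would classify every one of these records correctly. The failing pattern is narrow and the tables are descriptive. Protocol 6.5.18 has IC pain medication taken during the study entered in an electronic diary with date and time, so partial dates should arise mainly in eCRF records of earlier treatment. One could add that the SAP elsewhere resolves missing information towards treatment: missing adverse-event severity after first dose becomes severe, and missing causality becomes related.

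The limits on scope and impact stand. The defence of the wording does not. The SAP states an order, and 17.8.2 expressly covers a start that was itself imputed, so the literal route leads to the wrong class. The appeal to caution also fails here, because the stop month is not missing: it is recorded and then overwritten, and the drug is also removed from the prior table.

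A reader might infer that every record with two partial dates is misfiled. The grid shows otherwise: the other start patterns with a known stop month stay prior. If the stop month is missing as well and the year is the insertion year, the drug is not known to have ended before insertion, so filing it as concomitant contradicts nothing recorded.

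**Conclusion.** The rules are wrong as written for one narrow record type, because two stated tie-breaks conflict and the stated order selects the one that contradicts recorded data. Every record of that type is misfiled if 17.8.2 governs, and none if 17.8.1 does. This rests on reading first dose as first insertion and on the rules being programmed in the order given. The number of such records cannot be estimated from the documents. A percentage would require assumed drug durations and an assumed rate of partial dates, for which the documents give no basis.

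Three stronger inferences are tempting, and the documents do not support them.

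- **That the pain result is affected.** The primary ANCOVA, its imputation and the MMRM in SAP 11.1 and 11.1.1 do not use medication dates. The effect is confined to the prior and concomitant medication tables in SAP 9.
- **That the rule creates apparent prohibited medication on Day 0.** Nothing says that imputed medication dates determine eligibility or protocol deviations.
- **That adverse-event dating in SAP 17.7 needs the same change.** There only a complete stop date caps an imputed start. However, adverse events are collected only from consent and screening lasts at most 4 weeks, so an event that began and ended in an earlier month with its start known only to the year would be marginal.

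**What to change.** Add one precedence sentence to SAP 17.8, for example: when both dates are partial and the recorded stop month and year fall before the month of first insertion, the imputed start may not be later than the imputed stop; the start is set to the stop as in 17.8.1, and the 17.8.2 sentence that raises the stop to an imputed start does not apply.

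The worked example then becomes start = stop = 29 Feb 2016 and is prior only. The failing row of the grid goes to 0 for all three insertion dates, and the other rows stay at 0.

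Leave the remaining 17.8.2 stop rules as they are. Imputing the stop first, to the latest date its recorded parts allow, would also resolve the conflict. But it would change rules that are not at issue: a year-only stop in the last-dose year, for instance, would become 31 December instead of taking the month and day of study exit.

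The cost is one sentence in the SAP and a small change to the date-imputation program before database lock. No new data are needed.
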